10.2. Withdrawal of Participants From Study

Participants must be withdrawn from the study for any one of the following reasons:

- The participant withdraws consent.
- The participant enrolls into another interventional clinical study in which an investigational treatment or approved therapy for investigational use is administered.
- The participant is unwilling or unable to comply with the protocol.

The reason for the participant's withdrawal from the study must be recorded in the participant's CRF.

CONFIDENTIAL

The information contained herein may not be used, disclosed, or published without the written consent of Biogen MA Inc.

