7.2.3. Follow-Up

Participants will return for their final visit, which will be 4 weeks after their last dose. Participants who withdraw from the study early will return for an Early Termination Visit, which will be 4 weeks after their last dose.

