10. DISCONTINUATION OF STUDY TREATMENT OR WITHDRAWAL OF PARTICIPANTS FROM THE STUDY

10.1. Discontinuation of Study Treatment

A participant must discontinue study treatment for any of the following reasons:

- The participant becomes pregnant. Study treatment must be discontinued immediately. Report the pregnancy according to the instructions in Section [15.4.1](#).
- The participant withdraws consent to continue study treatment.
- The participant experiences a medical emergency that necessitates permanent discontinuation of study treatment.
- The participant is unwilling or unable to comply with the protocol.
- At the discretion of the Investigator or Sponsor.

The reason for discontinuation of study treatment must be recorded in the participant's CRF.

Participants who discontinue study treatment will be encouraged to remain in the study and complete all applicable protocol-specified tests and assessments. In circumstances when onsite visits are not possible, these assessments may be conducted by telephone.

Participants who terminate from the study early (i.e., discontinue both study treatment and study assessments) should complete the Final or Early Termination Visit. Home assessments will be allowed with Investigator approval for participants who are unable to complete the Final or Early Termination Visit at the site.

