13.1. Clinical Function Assessments

The following clinical assessments will be performed to evaluate the clinical function of BIIB067. See Section 4 for the timing of assessments. All study visits are expected to occur at the site, unless the participant is unable to travel to the site; then, a home visit may be possible at the discretion of the Investigator.

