15.3.2. Serious Adverse Events

Any SAE experienced by the participant between the time of the signing of the ICF and the final study visit is to be recorded on an SAE form, regardless of the severity of the event or its relationship to study treatment. SAEs must be reported to the Sponsor within 24 hours or according to national law as described in Section 15.3.3. Follow-up information regarding an SAE also must be reported with 24 hours.

Participants will be followed for all SAEs until the final study visit. Thereafter, the event should be reported to the Sponsor only if the Investigator considers the SAE to be related to study treatment.

Any SAE that is ongoing when the participant completes or discontinues the study will be followed by the Investigator until the event has resolved, stabilized, or returned to baseline status.

CONFIDENTIAL

The information contained herein may not be used, disclosed, or published without the written consent of
Biogen MA Inc.

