16.2. Clinical Function

16.2.1. Methods of Analysis

As this is an open-label, long-term extension study, analyses will be exploratory and descriptive in nature.

Data will be summarized using descriptive statistics for continuous variables and using frequency and percentage for discrete variables. For participants who have completed Parts A or B of Study 233AS101, the time trajectory of each clinical function may be summarized at selected timepoints and presented in plots. For participants who have completed Part C of Study 233AS101, the time trajectory will be summarized by the prespecified subgroup (enriched population versus other eligible participants) and the prior treatment received during Study

CONFIDENTIAL

The information contained herein may not be used, disclosed, or published without the written consent of Biogen MA Inc.

233AS101 from the baseline of Study 233AS101 (including data from Studies 233AS101 and 233AS102), from the baseline of Study 233AS102 (including data from Study 233AS102 only), and from the start of BIIB067 100 mg dosing.

Efficacy will be measured based on changes in ALSFRS-R, percent predicted SVC, HHD Megascore and individual muscle strength, [REDACTED]. Changes from baseline (using definitions outlined above) will be summarized over time for each of these endpoints.

Analysis of covariance using multiple imputation will be performed at selected timepoints, based on level of data available at interim and final analysis.

Time to death or permanent ventilation (i.e., ≥ 22 hours of mechanical ventilation [invasive or noninvasive] per day for ≥ 21 consecutive days) and time to death will be summarized using Kaplan-Meier curves based on the starting time using the following:

1. Entry into Study 233AS101
2. Entry into Study 233AS102
3. The start of BIIB067 100 mg dosing
4. Time of symptom onset

The relationship between PK or PD endpoints and the clinical function endpoints will also be explored.

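### No vital-status check follows early withdrawal, so time to death may be censored informatively and survival may be overstated

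*Protocol*

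**What the plan says.** **Endpoints and method.** Protocol Section 6.2.4 lists time to death, and time to death or permanent ventilation, as secondary efficacy endpoints. Under Section 16.2.1, "time to death will be summarized using Kaplan-Meier curves", and the composite is treated the same way. No censoring rule is stated.

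**Leaving the study.** Section 10.2 opens with "Participants must be withdrawn from the study for any one of the following reasons". One of those reasons is "The participant is unwilling or unable to comply with the protocol". Section 10.1 gives the same reason for stopping treatment, but then says "Participants who discontinue study treatment will be encouraged to remain in the study and complete all applicable protocol-specified tests and assessments", and adds "In circumstances when onsite visits are not possible, these assessments may be conducted by telephone". Section 13.1 says that, for someone who cannot travel, "a home visit may be possible at the discretion of the Investigator".

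**Last contact.** Section 7.2.3: "Participants who withdraw from the study early will return for an Early Termination Visit, which will be 4 weeks after their last dose".

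**Deaths.** Section 15.3.2: "Participants will be followed for all SAEs until the final study visit". After that visit, serious events are to be reported only if judged related to treatment, although events still open when a participant leaves are followed further. Section 15.3.3.1 requires every cause of death to be reported within 24 hours of the site learning of it, with no stated end date and no causality condition.

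**Analysis.** SAP Sections 3.5, 4.8.1 and 5 move efficacy out of the standalone report and into the integrated analysis, whose SAP is a separate document not supplied here. SAP Section 4.6 accepts a date of death from any available source, but only to define time on study.

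**The concern.** Kaplan-Meier assumes that a participant censored at a given time has the same future risk of death as those still followed. Treatment is by lumbar puncture every 4 weeks for years, in a disease that the protocol describes as inevitably progressive. Those who can no longer comply are likely to include people close to death. SAP Section 1 says that progression during washout and at lower doses led to many discontinuations among Parts A and B participants.

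If these participants leave, and their later deaths are judged unrelated to treatment (as a death attributed to ALS usually would be), the plan does not make anyone find out. Such deaths drop out of the numerator and the curve sits too high. The same records feed the integrated analysis. That analysis can state a censoring rule, but it cannot recover deaths that nobody was asked to collect.

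**Working it through.** The documents give no death rate, withdrawal rate, event count or survival estimate on this point, so there is no planned figure to reproduce. The first step below compares the texts. The remaining steps are illustrations on assumed inputs.

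**1. What happens to each kind of participant**

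| Participant | Last planned contact | Later death | Censoring |
|---|---|---|---|
| Completes the study | 4 weeks after the last dose, which the study calendar sets (Section 7.4) | Not sought | Administrative, so no bias by itself |
| Stops treatment, stays in study (10.1) | Continues, by telephone or home visit if needed | Captured | None added |
| Withdrawn early (10.2) | 4 weeks after last dose | Not sought; reportable if related (15.3.2), or if the site hears of it (15.3.3.1) | Possibly informative |

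Only the third row matters. For a participant unable to comply, Sections 10.1 and 10.2 point to different rows.

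**2. Withdrawal shortly before death**

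Assume true 3-year survival of 60% with constant hazard h = −ln(0.60)/3 = 0.170 per year. Assume a fraction p of all deaths is preceded by withdrawal 0 to 6 months earlier and goes unrecorded. The observed hazard is then close to (1−p)h, so the curve is close to 0.60^(1−p):

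- p = 10%: 0.60^0.9 = 0.631 (simulated 0.63)
- p = 20%: 0.60^0.8 = 0.665 (simulated 0.66)
- p = 30%: 0.60^0.7 = 0.699 (simulated 0.70)

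Here p is a share of deaths, not of participants. The deaths missed by year 3 are p × (1 − 0.60), that is 4%, 8% and 12% of participants.

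**3. Withdrawal at a steady rate, then a different death rate**

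Let w be the withdrawal rate and k the ratio of the death hazard after withdrawal to that before it. Censoring at withdrawal gives exp(−ht). True survival is

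S = exp(−(h+w)t) + w[exp(−kht) − exp(−(h+w)t)]/(h+w−kh).

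With h = 0.1703 and t = 3, the curve shows 60% in every case.

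- w = 0.1, k = 2: 0.4445 + 0.1 × (0.3600 − 0.4445)/(−0.0703) = 0.565, so about 56%
- w = 0.2, k = 2: 0.3293 + 0.2 × (0.3600 − 0.3293)/0.0297 = 0.536, so about 54%
- k = 1: 60%, no bias
- k = 0.5: 0.4445 + 0.1 × (0.7746 − 0.4445)/0.1851 = 0.623 and 0.3293 + 0.2 × (0.7746 − 0.3293)/0.2851 = 0.642, so the curve is too low

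**4. The same formula at Week 152**

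Take t = 152/52.18 = 2.91 years. Assume median survival of 2 or 5 years (Protocol Section 5.1 gives 2 to 5 years after diagnosis for most patients; using that range for time in study is an assumption). Assume cumulative withdrawal of 10% to 30% in the absence of death.

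| k | Curve minus truth, percentage points |
|---|---|
| 0.5 | −0.7 to −3.5 |
| 1 | 0 |
| 2 | +1.2 to +4.3 |
| 4 | +2.5 to +8.8 |

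Example: median 2 years, 30% withdrawal and k = 4 give a curve value of 36.4% against a true 28.7%.

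**The case against.** The strongest reply is that the plan already keeps declining participants in view. Section 10.1 encourages them to stay, telephone and home assessments are allowed, open serious events are followed after departure, and Section 15.3.3.1 covers all deaths without a time limit. The survival analyses are descriptive, and the censoring rule may stand in the integrated SAP.

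Much of this stands, and it rules out several stronger readings that a reader might infer:

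- **That deaths after the final visit are not collected.** Related deaths are reportable, open serious events are followed, and Section 15.3.3.1 can be read to cover any death the site learns of. The gap is that nobody has to ask, and that Section 15.3.2 narrows what is reported.
- **That survival is overstated as a matter of fact.** This needs leavers to die faster than those retained. That is likely in ALS, but the documents give no rate that shows it.
- **That all participants are affected.** Completers are not.
- **That the early-start versus delayed-start comparison is biased in a known direction.** That depends on withdrawal differing between groups and cannot be signed here.

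What the reply does not remove: remote follow-up helps only those who remain in the study, and Section 10.2 has no exception for progression. Follow-up of an open event may end when it stabilizes, and someone who leaves with no open event is not covered. The death date from any source in SAP Section 4.6 uses data already held. A descriptive curve can still be biased.

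**Conclusion.** The concern holds for early withdrawals. The plan makes withdrawal mandatory for a reason that disease progression can cause, requires no vital-status check afterwards, and uses a method that assumes withdrawal is unrelated to prognosis. Informative censoring is plausible and upward bias is the likely direction, so survival may be overstated.

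The size is unknown. On the assumed inputs above, the overstatement is about 3 to 10 points at 3 years when 10% to 30% of deaths go unrecorded after withdrawal. It is about 4 to 6 points with withdrawal of 10% to 20% per year and a doubled death rate afterwards. Equal hazards give no bias, and slower deaths among leavers reverse it. All of these figures assume constant hazards and that no death after withdrawal is captured. Any captured through Section 15.3.3.1 would shrink them.

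**What to change.** 1. At a common study-close cut-off, obtain last known vital status and its date for every dosed participant who has not refused such contact, by telephone or public record, whatever the cause of death.
2. Use it in time to death, and in the death component of the composite, in the integrated analysis. A vital-status check does not recover permanent ventilation after withdrawal, so the report should say how that component is censored.
3. State the censoring rule for both endpoints and add a sensitivity analysis for withdrawal, for example varying k as above.
4. Reconcile Section 10.1 with 10.2 for participants unable to comply, and Section 15.3.2 with 15.3.3.1 for deaths after the final visit. Which withdrawal rule should apply is for the sponsor and investigators to settle; the vital-status check does not depend on it.

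The cost is consent and protocol wording, plus about one contact or record check per withdrawn participant.

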11. STUDY TREATMENT USE

11.1. Regimen

11.1.1. Participants Who Have Completed Parts A or B of Study 233AS101

Participants will receive 3 loading doses of BIIB067, approximately 2 weeks apart, during the first 4 weeks, and up to 90 maintenance doses of BIIB067, approximately every 4 weeks, by IT injection.

All participants who were not receiving the 100 mg dose of BIIB067 will be dosed at BIIB067 100 mg at their next scheduled Maintenance Dose Visit.

11.1.2. Participants Who Have Completed Part C of Study 233AS101

Participants will not have a washout period. Participants who received placebo while in Part C of Study 233AS101 will receive 3 loading doses of BIIB067 100 mg approximately once every 2 weeks (Days 1, 15, and 29), while participants who received BIIB067 in Part C of Study 233AS101 will receive 2 doses of BIIB067 100 mg, on Days 1 and 29, and placebo on Day 15. All participants will receive BIIB067 100 mg at each Maintenance Dose Visit (up to 58 doses) thereafter. Study treatment administered to participants during the Loading Dose Period is to be blinded.

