Participants who have completed Part C of Study 233AS101 will have a blinded Loading Dose Period, during which participants who received BIIB067 in Study 233AS101 will receive 2 doses of BIIB067, on Days 1 and 29, and placebo on Day 15, and participants who received placebo in Study 233AS101 will receive 3 doses of BIIB067, on Days 1, 15, and 29.

For all participants, the Loading Dose Period will be followed by an unblinded maintenance dose portion of the study, during which participants will receive up to 90 doses of BIIB067, approximately every 4 weeks.

Study Location:

Approximately 42 sites are planned in approximately 15 countries globally.

Number of Planned Participants:

The sample size of this extension study is based on the sample size of the SOD1-ALS population in

CONFIDENTIAL

The information contained herein may not be used, disclosed, or published without the written consent of Biogen MA Inc.

Study 233AS101. Up to 183 participants will be dosed in Study 233AS101.

Study Population:

This study will be conducted in participants at least 18 years of age with SOD1-ALS who have completed Study 233AS101.

Detailed criteria are described in Section [8](#).

Treatment Groups:

BIIB067 100 mg will be administered by IT injection.

Duration of Study Participation:

The total duration of study participation for a single participant will vary and be up to 368 weeks, consisting of an approximately 4-week screening period; up to a 360-week treatment period; and a 4-week follow-up period.

CONFIDENTIAL

The information contained herein may not be used, disclosed, or published without the written consent of Biogen MA Inc.

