4. SCHEDULE OF ACTIVITIES FOR STUDY 233AS102

CONFIDENTIAL

The information contained herein may not be used, disclosed, or published without the written consent of
Biogen MA Inc.

Table 1: Schedule of Activities

Assessments	Screening Visit ¹	Baseline/1 st Loading Dose Visit			2 nd Loading Dose Visit			3 rd Loading Dose Visit			Maintenance Dose Visit			Final or Early Termination Visit 4 weeks after last dose	
	Week -4 to Day -1	Day 1			Day 15 (± 3 days) (Week 2)			Day 29 (± 3 days) (Week 4)			Weeks 8, 12, 16, and every 4 weeks thereafter up to Week 360 (± 3 days)				
		Pre dose	LP	Post dose	Pre dose	LP	Post dose	Pre dose	LP	Post dose	Pre dose	LP	Post dose		
ICF (main) and Genetic/Future Scientific Research Consent (optional) ²	X														
Medical History	X	X													
Confirmation of Eligibility Criteria ³	X														
Ventilation Use ⁴	X	X			X			X			X			X	
ALSFRS-R		X ⁵			X ⁵			X ⁵			X ^{5, 6}			X ⁵	
SVC ⁷		X ⁵			X ⁵			X ⁵			X ^{5, 8}			X ⁵	
HHD		X ⁵			X ⁵			X ⁵			X ^{5, 8}			X ⁵	
C-SSRS ¹²			X					X			X ⁶			X	

CONFIDENTIAL

The information contained herein may not be used, disclosed, or published without the written consent of Biogen MA Inc.

Assessments	Screening Visit ¹	Baseline/1 st Loading Dose Visit			2 nd Loading Dose Visit			3 rd Loading Dose Visit			Maintenance Dose Visit			Final or Early Termination Visit
	Week -4 to Day -1	Day 1			Day 15 (± 3 days) (Week 2)			Day 29 (± 3 days) (Week 4)			Weeks 8, 12, 16, and every 4 weeks thereafter up to Week 360 (± 3 days)			4 weeks after last dose
		Pre dose	LP	Post dose	Pre dose	LP	Post dose	Pre dose	LP	Post dose	Pre dose	LP	Post dose	
Weight	X	X												X
Vital Signs (temperature, blood pressure, pulse rate, respiratory rate)	X	X		X	X		X	X		X	X		X	X
12-lead ECG ¹³	X	X												X
Physical Examination ¹⁴	X	X												X
Limited Neurological Examination ¹⁴	X	X												X
Pregnancy Test ¹⁵	X	X			X			X			X			X
CSF Samples ¹⁶		X ¹⁷			X ¹⁷			X ¹⁷			X ¹⁷			
Clinical Laboratory Samples for Hematology, Coagulation, Chemistry, and Urinalysis ³	X	X			X			X			X			X
Blood Samples for Plasma anti-BIIB067 Antibody		X			X			X			X ¹⁸			X
Blood Samples for PK		X			X			X			X ¹⁸			X
Blood Samples for PD and Biomarkers		X			X			X			X			X
Blood Samples for DNA ¹⁹											X			
Blood Samples for RNA Analysis (optional) ²⁰		X			X			X			X			X
Study Treatment Administration			X		X			X			X			

CONFIDENTIAL

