7. STUDY DESIGN

7.1. Study Overview

This is a multicenter, open-label, long-term extension study to assess the long-term safety, tolerability, PK, PD, and efficacy of BIIB067 administered by IT injection to previously treated participants with SOD1-ALS who have completed Parts A, B, or C of Study 233AS101. The study will be conducted at approximately 42 sites in approximately 15 countries globally.

Participants who have completed Parts A or B of Study 233AS101 will have a washout period of at least 4 times the $t_{1/2}$ (~16 weeks) from the time of their last dose of study treatment in Study 233AS101 to their first dose in Study 233AS102. These participants will receive 3 loading doses of BIIB067 100 mg, approximately 2 weeks apart, during the first 4 weeks.

Participants who have completed Part C of Study 233AS101 will not have a washout period. To preserve the blinding used in Study 233AS101 until database lock, participants who enroll in Study 233AS102 after completing Part C of Study 233AS101 will have a blinded Loading Dose Period. Participants who received placebo while in Study 233AS101 will receive 3 doses of BIIB067 100 mg, approximately once every 2 weeks (Days 1, 15, and 29), while participants who received BIIB067 in Study 233AS101 will receive 2 doses of BIIB067 100 mg, on Days 1 and 29, and placebo on Day 15.

After the Loading Dose Period, participants will receive up to 90 maintenance doses of BIIB067 100 mg, approximately every 4 weeks until the last participant enrolled has had the opportunity to have their Week 152 Maintenance Dose Visit. Participants who were not receiving BIIB067 100 mg (i.e., participants in Parts A and B) will be dosed at BIIB067 100 mg at their next scheduled Maintenance Dose Visit.

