7.2.2.2. Maintenance Dose Period

During the maintenance portion of the study, participants will receive up to 90 doses of BIIB067, approximately every 4 weeks, during visits at Weeks 8, 12, and 16 and every 4 weeks thereafter until the last participant enrolled has had the opportunity to have their Week 152 Maintenance Dose Visit.

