7.4. End of Study

The end of study is last participant, last visit (approximately 4 weeks after their last dose). The last Maintenance Dose Visit for a participant will occur when the last participant enrolled has had the opportunity to have their Week 152 Maintenance Dose Visit.

CONFIDENTIAL

The information contained herein may not be used, disclosed, or published without the written consent of Biogen MA Inc.

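### Protocol 11.1.2 still caps Part C maintenance dosing at 58 doses, while the rest of the protocol and the SAP allow up to 90

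*Protocol*

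**What the plan says.** Protocol 11.1.2 is the regimen section for participants from Part C. After the blinded loading doses it states: "All participants will receive BIIB067 100 mg at each Maintenance Dose Visit (up to 58 doses) thereafter".

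The other current text differs:

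- **Protocol Synopsis, Study Design:** the limit is 90 maintenance doses, and the sentence that sets it covers everyone: "For all participants, the Loading Dose Period will be followed by an unblinded maintenance dose portion of the study".
- **Protocol Table 1:** Maintenance Dose Visits at Weeks 8, 12, 16 and "every 4 weeks thereafter up to Week 360".
- **Protocol 7.1:** "participants will receive up to 90 maintenance doses of BIIB067 100 mg".
- **Protocol 7.2.2.2:** also up to 90 doses, given "every 4 weeks thereafter until the last participant enrolled has had the opportunity to have their Week 152 Maintenance Dose Visit".
- **Protocol 7.4:** repeats the stopping rule without a dose count: "The last Maintenance Dose Visit for a participant will occur when the last participant enrolled has had the opportunity" for the Week 152 visit.
- **Protocol 11.1.1 (Parts A and B):** "up to 90 maintenance doses of BIIB067, approximately every 4 weeks, by IT injection".
- **SAP 2.2 and 3.3.2.2:** up to 90 doses with the same Week 152 stopping rule. SAP 2.2 applies this to all subjects.

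None of the statements that apply to the whole study makes an exception for Part C.

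**The concern.** Two current sections give a site different maximum numbers of intrathecal doses for the same Part C participant. The lower number stands in the section written specifically for that participant's regimen. Because 11.1.1 says 90 for Parts A and B, Section 11.1 reads as if the cap depended on which part the participant came from. Nothing else in the protocol or SAP supports that.

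The conflict could do harm in two ways:

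- **Early stopping.** A site that follows 11.1.2 literally would stop an early Part C entrant before the rule in 7.2.2.2 and 7.4 does. Under 7.2.3 the final visit follows 4 weeks after the last dose, and 11.4 provides no treatment after the study. Treatment and on-study safety follow-up would both end early.
- **Deviation logging.** A site that follows 7.2.2.2 gives doses after the 58th that depart from the wording of 11.1.2. These could be recorded as protocol deviations, and SAP 4.4 lists all deviations.

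**Working it through.** **1. Where 58 comes from.** The number of 4-weekly visits from week a to week b is (b − a)/4 + 1.

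- Week 8 to Week 236, the schedule before Version 6: (236 − 8)/4 + 1 = **58**, exactly the figure in 11.1.2.
- Week 8 to Week 360, the current Table 1: (360 − 8)/4 + 1 = **89**, which fits under a ceiling of 90 and does not match 58.
- Difference: 89 − 58 = 31 visits, and 31 × 4 = 124 weeks. This equals the extension that the Version 6 amendment summary states.

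The amendment history is used here only to trace the number. The Version 4 summary shows 58 in both 11.1.1 and 11.1.2. The Version 6 summary extends dosing for all participants and names Section 11.1 as affected. In the current text 11.1.1 carries 90 and 11.1.2 still carries 58.

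**2. Who could lose doses.** Suppose a participant starts g weeks before the last participant. When the last participant reaches Week 152, this participant is at Week 152 + g.

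- Maintenance visits scheduled by then: floor((152 + g − 8)/4) + 1.
- Excess over 58: floor((g − 84)/4).
- With m missed doses, doses lost under a literal cap: max(0, floor((g − 84)/4) − m).

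| Gap g (weeks) | Visits scheduled | Lost, m = 0 | Lost, m = 3 | Lost, m = 6 |
|---|---|---|---|---|
| 84 | 58 | 0 | 0 | 0 |
| 87 | 58 | 0 | 0 | 0 |
| 88 | 59 | 1 | 0 | 0 |
| 104 | 63 | 5 | 2 | 0 |
| 120 | 67 | 9 | 6 | 3 |
| 133 | 70 | 12 | 9 | 6 |

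The cap therefore bites only from a gap of 88 weeks.

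**3. Upper bound on the gap.** The documents give no entry dates. SAP 2.3 says Part C enrolment began under protocol Version 4.0, dated 11 January 2019. Version 6 is dated 04 August 2021. Assume the last participant had started by the Version 6 date. The largest possible Part C gap is then 936 days, and 936/7 = 133.7 weeks. This gives floor((133.7 − 84)/4) = floor(12.4) = **12** doses with none missed, and 9 or 6 with 3 or 6 missed.

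**4. Effect on the analysis.** SAP 4.6 takes expected doses from each subject's actual duration of dosing. For early withdrawals, the compliance denominator is the doses planned before withdrawal. Neither uses 58, and SAP 2.2 already states 90.

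**The case against.** The strongest reply is that this is an unrevised parenthesis whose intended meaning can be recovered. Section 11.1.2 ties dosing to each Maintenance Dose Visit, and Table 1, 7.2.2.2 and 7.4 define those visits for everyone. Section 11.2 also points to 7.2.2, which contains the 90-dose rule. A careful reader would probably use 90. That is fair, but 11.2 concerns dose modification and does not clearly say which dose count prevails. A section specific to Part C can reasonably be read as controlling.

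Further points:

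- **Twelve is a ceiling.** It needs a Part C participant to start on the Version 4 date itself, although amendments first need ethics approval, and to miss no dose. No document shows a Part C gap of 88 weeks or more. This stands.
- **Dosing may be over.** If the last participant started by 04 August 2021, Week 152 falls 152 × 7 = 1,064 days later, by 3 July 2024. The SAP was approved on 5–6 August 2024. On that assumption a text correction would guide no further dosing, and a clarification note is what remains useful.
- **Deviations are only a possibility.** Nothing shows that a dose at a scheduled visit would be logged as one. This stands.
- **Ninety is not exact.** The Week 8 to Week 360 schedule has 89 visits, and a 90th would fall at Week 364. That is a separate small point: an upper limit of 90 is not breached by 89 visits, and it is the figure used elsewhere.
- **Section 5.5 still mentions 22 maintenance doses.** That is dosing rationale, not the regimen instruction.

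These points limit the weight of the problem. None removes the contradiction.

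**Conclusion.** The concern holds. Protocol 11.1.2 gives a wrong dose limit for Part C, carried over from the Week 236 schedule, and it contradicts the Synopsis, 7.1 and 7.2.2.2 and SAP 2.2 and 3.3.2.2. It should be fixed because it is a dosing instruction, but the consequence is narrow.

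The per-participant loss under a literal reading runs from 0 to at most 12 intrathecal doses. That ceiling rests on three assumptions: the version dates bound the entry dates, the last participant had started by 04 August 2021, and no doses were missed. How many Part C participants are affected cannot be found from the documents and may be none. Endpoints, analysis sets and planned analyses are unaffected. The reach is limited to dosing instructions and deviation classification.

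**What to change.** In Protocol 11.1.2, change the limit from 58 to 90 doses and cross-refer to the Week 152 stopping rule in 7.2.2.2. Using 90 keeps 11.1.2 in line with 11.1.1, the Synopsis, 7.1 and the SAP.

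If dosing has already ended, issue a short clarification that the 90-dose limit and Week 152 rule governed Part C throughout, so that doses beyond the 58th are not classed as deviations.

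The cost is one number and one cross-reference, or one brief note. Data, endpoints, analysis sets and the SAP stay as they are.
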